5.5. Analysis of safety and reactogenicity

5.5.1. Analysis of safety and reactogenicity planned in the protocol

5.5.1.1. Analysis of Solicited Adverse events

All safety analyses will be performed using the Exposed set.

- Frequencies and percentages of subjects experiencing each AE will be presented for each symptom severity. Summary tables showing the occurrence of any local or systemic AE overall and at each time point will also be presented.

- Post-vaccination solicited AEs reported from Day 1 (of vaccination) to Day 7 will be summarized for the intervals Day 1-3, Day 4-7, Day 1-7 by maximal severity and by group, excluding the 30-minute measurement, which will be summarized separately. The severity of solicited local AEs, including injection-site erythema, induration and swelling will be summarized according to categories based on linear measurements as presented in [Table 6](#) below.
- Injection site pain and systemic AEs (including fever) occurring up to 7 days after each vaccination will be summarized according to “mild”, “moderate” or “severe”.
- Each solicited local and systemic AE will also be further summarized as “none” versus “any”.
- Use of antipyretics and analgesics will be summarized by frequency by type of use (prophylactic versus treatment) and percentage of subjects reporting use.
- Body temperature will be summarized by 0.5 °C increments from 38.0 °C/100.4°F up to ≥ 40 °C/104.0°F and will be broken down accordingly by route of measurement.
- Descriptive statistics (i.e., mean, median, minimum, maximum, low and upper quartiles) of the duration (in days) of solicited local (administration site) and systemic adverse events following each vaccination and overall will be provided by study group and for each solicited reaction.
- Descriptive statistics (i.e., mean, median, minimum, maximum, low and upper quartiles) of day of onset for solicited local (administration site) and systemic adverse reaction following each vaccination and overall will be provided by study group and for each solicited reaction.

Implausible measurements (for further definition see eDiary specification) will be left out of the analysis.

In the event of duplicate solicited AEs being reported both in the study eCRF and the eDiary, the Investigator's assessment will be prioritized for the main analysis.

For participants who have more than one solicited local (i.e., injection site pain, erythema, swelling, induration) or systemic (i.e., fever [temperature ≥ 38.0 °C], nausea, fatigue, myalgia, arthralgia, headache) measurement on a day, all data is listed. For the analysis, the worst measurement is analysed. For example, if for a participant a temperature of 38.5°C and 39.0°C is recorded on one day, both values are listed, for the analysis the 39.0°C is analysed.

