4.2. Exposed Set

All subjects that received at least one dose of the study treatment. The allocation to a group is done in function of the administered treatment.

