4.5.2. Elimination from Per-protocol analysis Set (PPS) and Full Analysis Set (FAS)

4.5.2.1. Excluded subjects

A subject will be excluded from the analysis under the following conditions

Table 4 Exclusion codes

Code	Condition under which the code is used	Visit (timepoints) where the code is applicable	Applicable for analysis set/endpoint
800	Fraudulent data	All	All
900	Invalid informed consent	All	All
1030	Study vaccine not administered at all	Visits 1, 3 and 4	All
1040	Administration of concomitant vaccine(s) forbidden in the protocol	Visit 1, 2 (before BS at M1)	PPS M1 and M3
1040	Administration of concomitant vaccine(s) forbidden in the protocol	Visit 2 (after BS at M1), 3, 4 (before BS at M3)	PPS M3
1050	Randomisation failure	Visit 1	PPS M1 and M3
1060	Randomisation code was broken	All	PPS M1 and M3
1070	Subjects got vaccinated with the correct vaccine but containing a lower volume	Visit 1	PPS M1

CONFIDENTIAL

205419 (MENB REC 2ND GEN-045 (V72_79))

Statistical Analysis Plan Amendment 3

Code	Condition under which the code is used	Visit (timepoints) where the code is applicable	Applicable for analysis set/endpoint
1070	Subjects got vaccinated with the correct vaccine but containing a lower volume	Visit 3	PPS M3
1070	Vaccination not according to protocol	Visit 1	PPS M1
1070	Vaccination not according to protocol	Visit 3	PPS M3
1080	Vaccine temperature deviation	Visit 1	PPS M1
1080	Vaccine temperature deviation	Visit 3	PPS M3
1090	Expired vaccine administered	Visit 1	PPS M1
1090	Expired vaccine administered	Visit 3	PPS M3
2010	Protocol violation (inclusion/exclusion criteria)	All	PPS M1 and M3
2040	Administration of any medication forbidden by the protocol	Visit 1, 2 (before BS at M1)	PPS M1 and M3
2040	Administration of any medication forbidden by the protocol	Visit 2 (after BS at M1), 3, 4 (before BS at M3)	PPS M3
2050	Not withdrawn after developing withdrawal criteria other than prohibited concomitant vaccination/medication (medical condition forbidden)	All	PPS M1 and M3
2060	Concomitant infection related to the vaccine which may influence immune response (only meningococcal infection)	All	PPS M1 and M3
2080	Subjects did not comply with vaccination schedule	Visit 1	PPS M1
2080	Subjects did not comply with vaccination schedule	Visit 3	PPS M3
2090	Subjects did not comply with blood sample schedule	Visit 2	PPS M1
2090	Subjects did not comply with blood sample schedule	Visit 4	PPS M3

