5.5.1.2. Analysis of eDiary compliance

eDiary compliance will be analysed as follows:

- The average percentage of eDiary entries will be reported by visit and overall, for each study group. The percentages of eDiary entries at subject level will be calculated and listed by visit.
- The numbers and percentages of participants who provided eDiary entries for the solicited local (administration site) and systemic adverse events during the 7 days after each vaccination (including the day of vaccination and excluding the 30-minute measurements) will be presented for each reporting day for each solicited reaction, by study group.
- The numbers and percentages of participants who reported eDiary entries for all the solicited local (administration site) and systemic adverse events, from Day 1 to Day 7 (for all 7 days), after each vaccination (including the day of vaccination and excluding the 30-minute measurements) will be reported by visit and by study group.
- The numbers and percentages of participants who provided eDiary entries for each solicited local (administration site) and systemic adverse events consecutively, for three days (day 1 through day 3 post-vaccination), 5 days (day 1 through day 5 post-vaccination) and 7 days (day 1 through day 7 post-vaccination), will be reported for each solicited reaction by visit and by study group.

Table 6 Intensity scales for solicited symptoms in adults and children of 6 years of age or more

Adolescents (from 11 years of age) and adults		
Adverse Event	Intensity grade	Parameter
Pain at injection site	0	None
	1	Mild: Any pain neither interfering with nor preventing normal every day activities.
	2	Moderate: Painful when limb is moved and interferes with every day activities.
	3	Severe: Significant pain at rest. Prevents normal every day activities.
Injection Site Induration, Swelling, Erythema	0	1 – 24 mm
	1	25 - 50 mm
	2	51 - 100 mm
	3	>100 mm
Temperature*	0	< 38.0°C (100.4°F)
	1	≥ 38.0 - 38.9°C (100.4 – 102.02°F)
	2	≥ 39.0 - 39.9°C (102.2 – 103.82°F)
	3	≥ 40.0°C (104.0°F)
Headache	0	Normal
	1	Mild: Headache that is easily tolerated
	2	Moderate: Headache that interferes with normal activity
	3	Severe: Headache that prevents normal activity
Fatigue	0	Normal
	1	Mild: Fatigue that is easily tolerated
	2	Moderate: Fatigue that interferes with normal activity
	3	Severe: Fatigue that prevents normal activity
Nausea	0	Normal

CONFIDENTIAL

205419 (MENB REC 2ND GEN-045 (V72_79))

Statistical Analysis Plan Amendment 3

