Adolescents (from 11 years of age) and adults		
Adverse Event	Intensity grade	Parameter
Generalized Myalgia	1	Mild: Nausea that is easily tolerated
	2	Moderate: Nausea that interferes with normal activity
	3	Severe: Nausea that prevents normal activity
	0	Normal
Generalized Arthralgia	1	Mild: Myalgia that is easily tolerated
	2	Moderate Myalgia that interferes with normal activity
	3	Severe: Myalgia that prevents normal activity
	0	Normal
	1	Mild: Arthralgia that is easily tolerated
	2	Moderate: Arthralgia that interferes with normal activity
	3	Severe: Arthralgia that prevents normal activity

*Fever is defined as temperature $\geq 38.0^{\circ}\text{C}/100.4^{\circ}\text{F}$. The preferred location for measuring temperature in this study will be the oral cavity for subjects.

Between groups assessment

No statistical tests for between-group comparisons will be performed.

The percentages of subjects with solicited local and systemic AEs during the 7 days (including the day of vaccination) following the first (Visit 1), the second (Visit 3) and the third (Visit 4) vaccination for all groups will be calculated.

Descriptive summary statistics will be provided by obesity status (i.e., BMI $<30\text{kg}/\text{m}^2$ vs $>30.\text{kg}/\text{m}^2$).

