5.5.1.3. Analysis of Unsolicited Adverse Events

All safety analyses will be performed using the Exposed set.

This analysis applies to all AEs occurring during the study, judged either as probably related, possibly related, or not related to vaccination by the investigator, recorded in AE eCRF, with a start date on or after the date of first vaccination. All AEs starting prior to the first vaccination will only be listed. The original verbatim terms used by investigators to identify AEs in the eCRFs will be mapped to preferred terms using the MedDRA dictionary. The AEs will then be grouped by MedDRA preferred terms into frequency tables according to system organ class.

All reported AEs, as well as AEs judged by the investigator as at least possibly related to study vaccine, will be summarized according to system organ class and preferred term within system organ class. These summaries will be presented by vaccination group and by interval of study observation. When an AE occurs more than once for a subject, the maximal severity and strongest relationship to the group will be counted.

Separate summaries will be produced for the following categories:

- Serious adverse events (SAEs)
- Adverse Events of Special Interest (AESIs) for subjects who received rMenB+OMV NZ

- Adverse events that are possibly or probably related to vaccine.
- Adverse event leading to withdrawal with relationship to COVID-19.
- Adverse events leading to a medically attended visit.

The frequencies and percentages of subjects who reported at least one immediate unsolicited adverse event (i.e., reactions that occurred during the first 30 minutes after any vaccination that have been flagged as immediate in the eCRF and have not been reported in the eDiary) following any study vaccination will be reported by study group.

Data listings of all AEs will be provided by subject. In addition, AEs in the categories above will be provided as listed data.

Between groups assessment

No statistical tests for between-group comparisons will be performed.

- The percentages of subjects with any unsolicited AEs (including all SAEs) during the 30 days (including the day of vaccination) following the first (Visit 1), the second (Visit 3) and the third (Visit 4) vaccination for all groups will be calculated.

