10.1.2.3. Daily recording of solicited adverse events

For the collection of solicited adverse events, a solicited adverse event will be considered present only when a daily recording of grade 1 or more is present.

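### Does placing all safety analyses on the Exposed Set turn missed doses and missing diaries into non-events?

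*SAP*

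**What the plan says.** Protocol 10.3.4 and SAP 5.5.1.1 and 5.5.1.3 place the safety analyses on one set. The SAP wording is "All safety analyses will be performed using the Exposed set", and SAP 4.2 defines the set as "All subjects that received at least one dose of the study treatment".

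The primary safety endpoints are reported per vaccination. The solicited 7-day percentages "following the first (Visit 1), the second (Visit 3) and the third (Visit 4) vaccination for all groups will be calculated", and SAP 5.5.1.3 asks for "The percentages of subjects with any unsolicited AEs (including all SAEs) during the 30 days" after the same three vaccinations. No denominator is attached to either.

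On missing diary data, SAP 10.1.2.3 says "a solicited adverse event will be considered present only when a daily recording of grade 1 or more is present". SAP 5.5.1.1 adds a two-way split into none or any: "Each solicited local and systemic AE will also be further summarized as" those two categories. SAP 5.5.1.2 reports diary completion separately: "The average percentage of eDiary entries will be reported by visit and overall, for each study group", with further counts by reporting day and by symptom. The table layouts are in a separate document (SAP 10.2).

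**The concern.** Subjects can be in the Exposed Set without a later dose. Protocol 7.7 stops further vaccination for contraindicated subjects but encourages them to stay in the study, and protocol 9.2 allows continued procedures after vaccine withdrawal. SAP 10.1.1 attaches an event to the most recent dose actually given. A subject without dose 2 can therefore never add an event to the dose 2 percentage, only a unit to its denominator.

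Diaries can also be missing. Protocol 12.5.8.1.1 sets site alerts for failure to enter or transmit data. The threshold rule in SAP 10.1.2.3 sits under the heading on missing data, so it can be taken to mean that no recording equals no event.

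If both were applied mechanically, the percentages after each vaccination would be too low. With no between-group tests for safety, those percentages are what readers will use. Protocol 12.5.8.2 adds to the doubt by still naming an unsolicited safety set that neither current document defines.

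**Working it through.** **The plan's own figures.** The documents give no expected reaction rate, no rate of missed doses or diaries, and no safety denominator, so there is no safety figure to reproduce. The only usable input is the group size. Protocol 10.1.2 inflates 250 evaluable subjects for 20% loss: 250 / (1 − 0.20) = 312.5, so 313, against the 315 planned.

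**Size under the literal reading.** Let p be the rate among subjects with the dose (and, for solicited events, a diary), and m the share of the Exposed Set without. Then

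reported rate = p × (1 − m).

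Both p and m are assumed.

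| m | subjects of 315 | p = 60% | p = 80% |
|---|---|---|---|
| 2% | 6.3 | 58.8% | 78.4% |
| 5% | 15.8 | 57.0% | 76.0% |
| 10% | 31.5 | 54.0% | 72.0% |
| 20% | 63.0 | 48.0% | 64.0% |

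The 20% row uses the only loss rate in the documents. It covers withdrawal and non-evaluability for immunogenicity, so it is an extreme value for m.

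**The concomitant-versus-alone comparison.** This is made at Visit 1. Everyone in the Exposed Set has at least one dose, so missed later doses do not enter. Only unequal diary loss at dose 1 could matter, and the apparent difference is p × (difference in m).

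- Gap of 5 points, p = 60%: 0.60 × 5 = 3.0 points. The 95% half-width at 315 per group is 1.96 × √(2 × 0.6 × 0.4 / 315) = 7.65 points.
- Gap of 10 points, p = 60%: 6.0 points, still inside 7.65.
- Gap of 10 points, p = 80%: 8.0 points, against 1.96 × √(2 × 0.8 × 0.2 / 315) = 6.25 points. A gap this wide would exceed sampling error.

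That last case needs a 10-point difference in diary return between blinded arms that each receive two injections at Visit 1. The completion tables by visit and group would show it.

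**Does the text require the literal reading?**

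1. Naming a set says who may enter an analysis. A percentage of subjects with events following the second vaccination presupposes that it was given.
2. The SAP already narrows within the Exposed Set: AESIs to rMenB+OMV NZ recipients, and Month 9 to 15 events to subjects followed for 12 months.
3. In SAP Table 6, grade 0 is a recorded grade, and for erythema, swelling and induration it covers 1 to 24 mm. A rule that an event needs grade 1 or more is therefore needed whether or not diaries are missing. It is silent on the subject with no entry.
4. The none-or-any split is additional to summaries by maximal severity, by measured size and by temperature band. A no-event cell can hold recorded grade 0 entries; nothing puts absent diaries there.
5. Elsewhere the SAP does not fill gaps favourably. Implausible measurements are left out (5.5.1.1), laboratory values are not replaced (10.1.2.2), and missing AE severity or relationship is shown as unknown (10.1.2.4).

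**The case for a change.** The strongest point against leaving the text alone is that these are primary endpoints and a SAP should state their denominators. The restrictions for AESIs and for Month 9 to 15 show that the authors did so where they thought of it, and their silence here could be read as intent. The literal effect can only lower the reported rates. Some subjects are also stopped because of a related SAE or a new AESI (protocol 7.7), so those left in a later dose's denominator may not be typical.

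The usual answers are incomplete. Elimination code 1030 lists Visits 1, 3 and 4, but its label is "Study vaccine not administered at all". Removing everyone who missed one dose would contradict the set's definition, so the code does not settle a per-dose count. The completion tables show the missing diaries without changing any AE percentage. Reactions reported only verbally go into the eCRF as unsolicited (protocol 12.5.8), so they are kept in the safety data but not in the solicited tables.

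What stands is that the denominator is unstated and that one sentence would have removed the doubt. What does not stand is that the plan directs analysts to count unexposed or unobserved subjects as event-free. A reader could also recover the intended rate from the diary completion counts and the vaccination counts in SAP 5.2.1, if those are tabulated by dose, which that section does not say.

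**Conclusion.** This is missing detail of a kind that analysts fill sensibly, and it needs no change to the plan. The natural implementation uses Exposed Set subjects who received the vaccination in question and, for solicited events, have diary data for it. The full set remains the denominator for whole-study SAE, medically attended AE and withdrawal summaries. The table layouts, which were not available, are where these counts would appear.

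If the literal reading were followed, an assumed 60% rate would fall by 1.2 to 6.0 points for 2% to 10% missing. The Visit 1 comparison would shift by 3.0 points for a 5-point gap in diary return, against a sampling half-width of 7.65 points. These figures assume that subjects without data react at the same rate as those observed. No success criterion uses the safety percentages, so neither power nor type I error is affected.

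The stray set name in protocol 12.5.8.2 is a clerical leftover. Protocol 10.3.4 and SAP Amendment 3 both put safety on the Exposed Set.

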5.5.1.2. Analysis of eDiary compliance

eDiary compliance will be analysed as follows:

- The average percentage of eDiary entries will be reported by visit and overall, for each study group. The percentages of eDiary entries at subject level will be calculated and listed by visit.
- The numbers and percentages of participants who provided eDiary entries for the solicited local (administration site) and systemic adverse events during the 7 days after each vaccination (including the day of vaccination and excluding the 30-minute measurements) will be presented for each reporting day for each solicited reaction, by study group.
- The numbers and percentages of participants who reported eDiary entries for all the solicited local (administration site) and systemic adverse events, from Day 1 to Day 7 (for all 7 days), after each vaccination (including the day of vaccination and excluding the 30-minute measurements) will be reported by visit and by study group.
- The numbers and percentages of participants who provided eDiary entries for each solicited local (administration site) and systemic adverse events consecutively, for three days (day 1 through day 3 post-vaccination), 5 days (day 1 through day 5 post-vaccination) and 7 days (day 1 through day 7 post-vaccination), will be reported for each solicited reaction by visit and by study group.

Table 6 Intensity scales for solicited symptoms in adults and children of 6 years of age or more

Adolescents (from 11 years of age) and adults		
Adverse Event	Intensity grade	Parameter
Pain at injection site	0	None
	1	Mild: Any pain neither interfering with nor preventing normal every day activities.
	2	Moderate: Painful when limb is moved and interferes with every day activities.
	3	Severe: Significant pain at rest. Prevents normal every day activities.
Injection Site Induration, Swelling, Erythema	0	1 – 24 mm
	1	25 - 50 mm
	2	51 - 100 mm
	3	>100 mm
Temperature*	0	< 38.0°C (100.4°F)
	1	≥ 38.0 - 38.9°C (100.4 – 102.02°F)
	2	≥ 39.0 - 39.9°C (102.2 – 103.82°F)
	3	≥ 40.0°C (104.0°F)
Headache	0	Normal
	1	Mild: Headache that is easily tolerated
	2	Moderate: Headache that interferes with normal activity
	3	Severe: Headache that prevents normal activity
Fatigue	0	Normal
	1	Mild: Fatigue that is easily tolerated
	2	Moderate: Fatigue that interferes with normal activity
	3	Severe: Fatigue that prevents normal activity
Nausea	0	Normal

CONFIDENTIAL

205419 (MENB REC 2ND GEN-045 (V72_79))

Statistical Analysis Plan Amendment 3

Adolescents (from 11 years of age) and adults		
Adverse Event	Intensity grade	Parameter
Generalized Myalgia	1	Mild: Nausea that is easily tolerated
	2	Moderate: Nausea that interferes with normal activity
	3	Severe: Nausea that prevents normal activity
	0	Normal
Generalized Arthralgia	1	Mild: Myalgia that is easily tolerated
	2	Moderate Myalgia that interferes with normal activity
	3	Severe: Myalgia that prevents normal activity
	0	Normal
	1	Mild: Arthralgia that is easily tolerated
	2	Moderate: Arthralgia that interferes with normal activity
	3	Severe: Arthralgia that prevents normal activity

*Fever is defined as temperature $\geq 38.0^{\circ}\text{C}/100.4^{\circ}\text{F}$. The preferred location for measuring temperature in this study will be the oral cavity for subjects.

Between groups assessment

No statistical tests for between-group comparisons will be performed.

The percentages of subjects with solicited local and systemic AEs during the 7 days (including the day of vaccination) following the first (Visit 1), the second (Visit 3) and the third (Visit 4) vaccination for all groups will be calculated.

Descriptive summary statistics will be provided by obesity status (i.e., BMI $<30\text{kg}/\text{m}^2$ vs $>30.\text{kg}/\text{m}^2$).

5.5.1.3. Analysis of Unsolicited Adverse Events

All safety analyses will be performed using the Exposed set.

This analysis applies to all AEs occurring during the study, judged either as probably related, possibly related, or not related to vaccination by the investigator, recorded in AE eCRF, with a start date on or after the date of first vaccination. All AEs starting prior to the first vaccination will only be listed. The original verbatim terms used by investigators to identify AEs in the eCRFs will be mapped to preferred terms using the MedDRA dictionary. The AEs will then be grouped by MedDRA preferred terms into frequency tables according to system organ class.

All reported AEs, as well as AEs judged by the investigator as at least possibly related to study vaccine, will be summarized according to system organ class and preferred term within system organ class. These summaries will be presented by vaccination group and by interval of study observation. When an AE occurs more than once for a subject, the maximal severity and strongest relationship to the group will be counted.

Separate summaries will be produced for the following categories:

- Serious adverse events (SAEs)
- Adverse Events of Special Interest (AESIs) for subjects who received rMenB+OMV NZ

- Adverse events that are possibly or probably related to vaccine.
- Adverse event leading to withdrawal with relationship to COVID-19.
- Adverse events leading to a medically attended visit.

The frequencies and percentages of subjects who reported at least one immediate unsolicited adverse event (i.e., reactions that occurred during the first 30 minutes after any vaccination that have been flagged as immediate in the eCRF and have not been reported in the eDiary) following any study vaccination will be reported by study group.

Data listings of all AEs will be provided by subject. In addition, AEs in the categories above will be provided as listed data.

Between groups assessment

No statistical tests for between-group comparisons will be performed.

- The percentages of subjects with any unsolicited AEs (including all SAEs) during the 30 days (including the day of vaccination) following the first (Visit 1), the second (Visit 3) and the third (Visit 4) vaccination for all groups will be calculated.
- The percentages of subjects with SAEs, AEs leading to withdrawal, and medically attended AEs, throughout the study period (Day 1 /Month 0 to Month 9) will be calculated. Among subjects who are followed for 12 months after their last dose the percentages of subjects with SAEs, AEs leading to withdrawal, and medically attended AEs, between SFU 5/Month 9 and SFU 7/Month 15 will also be calculated.
- The percentages of subjects with AESI throughout the study period (Day 1 /Month 0 to Month 9) will be calculated (for subjects who received rMenB+OMV NZ). Among subjects who are followed for 12 months after their last dose the percentages of subjects with AESI, between SFU 5/Month 9 and SFU 7/Month 15 will also be calculated.

Descriptive summary statistics will be provided by obesity status (i.e., BMI <30kg/m² vs >30.kg/m²).

